	 Patients with existing gastrostomy and jejunostomy enteral feeding tubes, placed ≥ 3 months, undergoing replacement of feeding tube inpatient or outpatient. Willing to adhere to placement of study stoma site accessory and ability to take oral temperature at specified times. Stated willingness to comply with all study procedures and availability for the duration of the study. Willing to adhere to removal of study stoma site accessory at mo. 6 Exclusion Criteria Patient requires general anesthesia in an OR for tube changes Current use of steroids (any dose) daily ≥ 3 months including, but not limited to: prednisone, prednisolone, methylprednisolone, cyclosporine Current use of Immunosuppressants including, but not limited to: azathioprine, mycophenolate. BMI ≥ 40 Non-English speaking patients. Pregnant Women. Known allergic reactions to components of the study stoma site accessory: Medical Grade Silicone as described in Technical Data Prospectus from Dow Corning Corporation. Treatment with another investigational drug or device within 6 months of screening/baseline. Uncontrolled illness, recent open abdominal surgery or social situations that in the opinion of the investigative team would limit compliance with study requirements, including, but not limited to: Ongoing or active infection Psychiatric illness Unable to self-report Not ambulatory and incapable of carrying out all self-care Unsuccessful study accessory placement at initial replacement procedure
Number of	The study will enroll until 10 patients have had successful study stoma
	site accessory placement and reached the 2 week research follow-up
Subjects	visit.
Number of Sites	1
Sample Size	The sample size is 10 subjects. No formal sample size calculations were
Justification	performed for pre-market safety and efficacy data.
Study Hypothesis	The study is a pilot trial to access feasibility and safety with the aim to improve patient quality of life using pre and post measures. Patient quality of life assessment will be collected at baseline and 6 months for comparison.

Duration of Study	Expected enrollment period is 12 months. Follow-up duration is 6 months from initial replacement procedure with follow-up research visit at week 2 and phone calls at weeks 4 and 6 and month 6 and research visits at months 3, 4 and 6. The study will conclude 6 months from the enrollment of the last subject.

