- 3. Abdominal Pictures will be taken using Haiku software on CC issued cellphones and uploaded securely to the patient electronic chart. Pictures can be sent by the patient in MyChart for virtual visits scheduled through MyChart. Virtual visit abdominal pictures and screen captures are optional if not feasible to obtain at any study time points. Pictures are optional for study participation.
- 4. Medications of interest are primarily antibiotics.
- 5. Intervention at the study site occurs within 30 days of Informed Consent.
- 6. Daily temperature log to be completed by patient on days 3 through 10 and reported at week 2 and at months 3 and 4. Temperatures are self-recorded for all virtual visits; collection of temperature log is not required. The patient will be asked to call their treating physician if the patient is reporting a temperature over 100.4°F.
- 7. General assessment of the abdomen with stoma site inspection occurs at baseline evaluation, week 2 and months 3, 4 and 6 research visits and early termination. The week 2 and months 3 and 4 research visit may be scheduled in person or virtually. When the exam is virtual, the patient will be asked to report body temperature and vitals and allow/provide a visual of the abdomen for assessment and pictures when applicable. Pictures are optional for study participation.
- 8. Additional labs, radiology or other medically necessary procedures at week 2, months 3, 4 and 6 or early study termination as determined by the attending physician are considered standard of care. Patients will be asked to contact the study coordinator within 48 hours of a qualifying event, e.g., removal of study stoma site accessory that occurs at an external medical facility leading to participant early study termination.
- 9. Study personnel will schedule a research visit for months 3, 4 and 6 Study visits week 2 and at months 3 and 4 can be conducted virtually or in person. The month 6 study visit will be conducted in person for purposes of accessory removal.
- 10. Patients will be asked to contact study personnel to schedule in-person study accessory removal when removal is voluntary.

Number of patients

Ten patients to be recruited at one site, the Cleveland Clinic Main Campus. Patients who are prematurely withdrawn prior to week 2 follow-up will be replaced until the total number of patients exceeding week 2 equals 10.

Study Duration

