Informed consent language will include description of allowance for the study investigator to determine that the patient is not a good candidate after consent and prior to, or at the time of intervention. Determination of inappropriateness will be made in the best interest of the patient. If such determination is made, the investigator will identify the decision directly with the patient. The patient will have acknowledged and agreed to this decision as part of the Informed Consent process. The patient will understand and agree that no additional financial compensation will be provided if they are considered ineligible. The patient will have acknowledged and agreed to an alternative, standard of care replacement or other procedure to be performed in their best interest.

Individuals who do not meet the criteria for inclusion in this trial because of a previously
undetermined condition of anatomical or medical origin may be rescreened at a later date if, a)
the study is still recruiting patients b) the previous condition has been resolved. Rescreened
participants should be assigned the same participant number as for the initial screening.

Minimal information including demography, eligibility criteria, screen failure details and any adverse event or serious adverse event (SAE) from the time of consent up to the intervention will be collected for Consolidated Standards of Reporting Trials publishing requirements and to respond to queries from regulatory authorities.

EARLY PATIENT WITHDRAWAL/STUDY TREATMENT DISCONTINUATION

A patient may voluntarily withdraw from the study at any time either before or after undergoing the initial replacement procedure without prejudice or loss of care. The patient should notify the investigator of his/her desire to withdraw. The Principal Investigator, or his/her designee, or in consultation with multiple study team personnel, may also decide to withdraw the patient from the study at any time based on medical judgment.

A patient should be withdrawn from the study if the Principal Investigator believes, or agrees in consultation with the study team and/ or Safety Officer recommendation that continuation would be detrimental to the patient's well-being. Reasons for Study Treatment Discontinuation/Early Patient Withdrawal are:

- Withdrawal of Informed Consent, (subject's decision to withdraw for any reason).
- Any clinically significant AE/SAE(s), laboratory abnormality, and/or concurrent illness which, in

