 the opinion of the investigator, indicates that continued treatment with study accessory and/or
 further participation in the study, is not in the best interest of the subject.
- Significant protocol violation.
- Protocol deviation resulting in significant patient safety risk.
- Subjects who for any reason cannot be followed and/or are unable to meet the requirements of the protocol.
- Death after consent

Patients who leave the study prior to month 6 voluntarily will be asked to schedule an in person, early termination visit for the study stoma site accessory removal and a standard of care tube replacement.

In all instances of withdrawal, the appropriate study visit and study termination data should be recorded in the electronic chart and should include the reason why the patient has been withdrawn from the study. Any data collected on the patient up to the point of withdrawal may be used in the analysis. Subjects who are prematurely withdrawn from the study prior to week 2 research follow-up will be replaced until 10 patients have been successfully recruited.

In the event a patient cannot be contacted for follow-up assessments, at least three attempts should be made to locate the patient, and these efforts will be documented. If the patient cannot be located, a lost to follow-up entry will be submitted for regulatory purposes.

COSTS AND COMPENSATION

The study stoma site accessory, week 2 interval assessments and months 3, 4 and 6 follow-up visits will be covered by the study, which will not be billed to the patient or their health insurance plan. These "research only" services that are paid for by the Clinic include: abdominal assessment not done for conventional standard care, removal of the study accessory at month 6 with replacement of standard, conventional tubing components and administration of study specific questionnaires. If additional medical services are performed during this research study that are considered to be conventional, routine clinical services that would have been performed even if the patient were not participating in the research study, these will be billed to the health insurance plan or the patient. Examples of these routine services include but are not limited to: CT scans, conventional care, drug and labs not required by the study and additional

feeding tube changes. The patient will be responsible for paying any deductibles, co-payments or coinsurance that are a normal part of their health insurance plan.

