accessory as evidenced by rate of	defined as placement of the device at	accessory viability; its			
successful device placement and	the intended location, including securing	safety and efficacy for			
related post procedure adverse	of the device in place and its	use in a general			
events.	effectiveness at the week two [2] exam.	population of patients			

OBJECTIVES	ENDPOINTS	JUSTIFICATION FOR ENDPOINTS
The study will focus on the known minor risks of tube leakage associated with feeding tube components including recurrence of any documented pre-procedure [abdominal surface] condition, new condition or repeat intervention up to 6 months after the initial replacement procedure.	Patients will be followed up to 6 months after the index procedure. However, any patient who requires re-intervention that compromises the study stoma site accessory integrity (e.g., study accessory is removed and replaced with standard of care components or otherwise damaged) subsequent to the initial replacement procedure will no longer be followed but will be included in the analysis of the endpoints until the time of re-intervention. Rate of post-procedure adverse events to be collected from initial replacement procedure through month 6, including but not limited to: Dermatitis Cellulitis Accessory migration over 1 cm An adverse event determined as related or possibly related Allergic reaction to the accessory material	displaying a broad range of disease processes for which they will be receiving EN or HEN for ≥ 3 months.
Secondary		
Change in patient quality of life after intervention as self-reported by participants. Outcomes will be collected at various intervals.	Various participant reported outcomes will be collected at baseline, week 2 and month 6: PROMIS 10, nationally validated quality of life survey tool Alcohol/ tobacco use Study accessory management questions Characteristics of pain and leakage at site of study accessory placement	Demonstrated ability to predict clinical benefit to patients with enteral feeding tubes.

Table 3

Hypothesis Testing

This is not a hypothesis driven study. The study is a pilot trial to determine safety and efficacy of a feeding tube accessory and feasibility of determining improvement of patient quality of life using pre and post measures. Patient quality of life assessment will be collected at baseline and 6 months for comparison.

Data Collection and Analysis

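### Patients who leave before week 2 are replaced, and no rule scores them or fixes the denominator, so week-2 effectiveness can be reported only in those who lasted that long

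*Combined protocol and SAP*

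**What the plan says.** **Who makes up the ten.** The synopsis counts a patient towards the target after successful "site accessory placement and reached the 2 week research follow-up" visit. The Number of patients section adds: "Patients who are prematurely withdrawn prior to week 2 follow-up will be replaced until the total number of patients exceeding week 2 equals 10". The section on early withdrawal and treatment discontinuation repeats this: "Subjects who are prematurely withdrawn from the study prior to week 2 research follow-up will be replaced until 10 patients have been successfully recruited". None of these distinguishes between causes of exit.

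**What causes exit.** The adverse event reporting section ends participation when the accessory malfunctions, is inadvertently removed or compromised, or is judged to carry more risk than benefit, and a commercial accessory replaces it. The withdrawal section's list of reasons includes the item that begins "Any clinically significant AE/SAE(s), laboratory abnormality, and/or concurrent illness which, in" and also death after consent. It further covers withdrawal of consent, protocol violation and inability to be followed.

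**What is measured.** In Table 3, procedural success means placement at the intended location, securing of the device, and its "effectiveness at the week two [2] exam".

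**Whose data are used.** The withdrawal section says: "Any data collected on the patient up to the point of withdrawal may be used in the analysis". Table 3 says that patients whose re-intervention compromises the accessory "will no longer be followed but will be included in the analysis of the endpoints until the time of re-intervention", and Study Duration has an equivalent rule.

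**How it is analysed.** Data Collection and Analysis promises frequencies, percentages and 95% confidence intervals. It names no analysis set, denominator or interval method.

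**The concern.** The point concerns patients in whom placement succeeded. Several reasons for leaving before week 2 are the outcomes that the primary endpoint exists to detect. A patient whose accessory comes out on day 5 exits, has no week-2 exam, and is replaced by a new patient. Nothing says whether that patient is a failure for week-2 effectiveness, a missing value, or outside the denominator.

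Because the target of ten consists by definition of patients who reached week 2, ten is a natural denominator and nothing rules it out. A rate on that base is conditional on having lasted two weeks. In a first-in-human device study of about ten patients, one omitted early failure visibly changes the main result, and early failures are among the things such a study most needs to show.

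**Working it through.** **The plan's own figure.** The synopsis says "The sample size is 10 subjects. No formal sample size calculations were" performed. The figure of ten has no effect size, precision target or dropout rate behind it, so there is nothing to reproduce. What can be checked is the effect of the replacement rule on the reported rate.

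**Set-up.** Let s be the number effective at week 2 among the 10 who reach it, and k the number placed successfully who exit earlier because of the accessory and are replaced.

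- Week-2 completers only: s/10.
- All placed, early failures counted as not effective: s/(10 + k).
- Difference: s/10 − s/(10 + k) = s·k / [10(10 + k)]. This is never negative, so the completer rate can only equal or exceed the all-placed rate.

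The documents give no values for s or k; those below are assumptions shown over a range. Intervals are exact (Clopper-Pearson), also an assumption because the plan names no method.

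| s | k | Completers only (95% CI) | All placed (95% CI) | Difference, points |
|---|---|---|---|---|
| 10 | 1 | 10/10 = 100% (69.2–100) | 10/11 = 90.9% (58.7–99.8) | 9.1 |
| 10 | 2 | 10/10 = 100% (69.2–100) | 10/12 = 83.3% (51.6–97.9) | 16.7 |
| 10 | 3 | 10/10 = 100% (69.2–100) | 10/13 = 76.9% (46.2–95.0) | 23.1 |
| 8 | 2 | 8/10 = 80.0% (44.4–97.5) | 8/12 = 66.7% (34.9–90.1) | 13.3 |

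With s = 10, the completer result is the same however many patients were replaced.

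**How often replacement would occur.** Let d be the assumed probability of exit before week 2 for any cause. The expected number placed to get 10 past week 2 is 10/(1 − d). The chance that at least one of the first 10 placed is replaced is 1 − (1 − d)^10.

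| d | 10/(1 − d) | Chance of at least one replacement |
|---|---|---|
| 5% | 10.5 | 40% |
| 10% | 11.1 | 65% |
| 20% | 12.5 | 89% |
| 30% | 14.3 | 97% |

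**Adverse events.** This rate is affected only if the permissive sentence is used to leave out early leavers. Suppose 12 are placed, both early leavers had an event, and so did 3 of the other 10. Leaving out the two gives 3/10 = 30% (6.7–65.2); keeping them gives 5/12 = 42% (15.2–72.3).

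**The case against.** The strongest reply is that the documents already protect the patients who matter most. Table 3 and Study Duration require inclusion when a re-intervention compromises the accessory, and Table 3's example, removal with substitution of standard components, covers most device failures that lead to exit. Repeat intervention is itself part of the primary endpoint, so a day-5 removal is recorded there. Table 1 schedules stoma inspection, the pain and leakage questionnaire and adverse events at early termination. Unscheduled visits that end in early termination are to be captured, and an independent Safety Officer reviews the data. The study is descriptive, with no success threshold.

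Much of this stands, and it defeats three stronger readings.

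- A reader might infer that use of all early leavers' data is optional. That is true of the general withdrawal sentence only, not of the re-intervention group.
- A reader might infer that the analysis is restricted to the ten. No section says so; the replacement rule governs when recruitment stops, and the denominator is left open.
- A reader might infer that the adverse-event rate is biased as planned. Events are to be collected from the procedure through month 6, and nothing directs that they be dropped.

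The reply does not close the gap. Inclusion up to the re-intervention does not say how a patient without a week-2 exam counts for week-2 effectiveness; such a patient can be included and still be missing for that component. Withdrawals for an adverse event or death without a re-intervention fall under the permissive sentence. Early-termination assessments are only to be attempted, and no text links them to the week-2 outcome. The early-termination list under Follow-Up also omits adverse events, although Table 1 marks them.

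**Conclusion.** The concern holds in a limited form. The replacement rule, the undefined denominator and the absence of a scoring rule together allow week-2 effectiveness to be reported in survivors to week 2 only. The direction of any resulting error is fixed: the rate is never understated relative to all placed patients with early failures counted. With all ten completers effective, one, two or three omitted failures overstate it by about 9, 17 or 23 points.

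These sizes rest on assumed counts and exact intervals. The documents give no early-exit rate, so whether any such patient will occur is unknown. Nor should every early exit be read as a device failure, since the listed reasons include consent withdrawal and concurrent illness. The conflict between the permissive and mandatory data-use rules is a matter of text and needs no assumption.

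**What to change.** Amend the Number of patients section, the withdrawal section, Table 3, and Data Collection and Analysis as follows.

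1. Keep replacement as a recruitment rule only. State that it does not remove anyone from the analysis.
2. State that every patient with a placed accessory is in the primary analysis, including those later replaced.
3. Count an exit before the week-2 exam as not effective at week 2 when it is due to accessory removal, malfunction or compromise, or to an adverse event, serious adverse event or death judged related or possibly related to the accessory.
4. List all other pre-week-2 exits separately, with their number and reason, and add a sensitivity analysis that counts them as not effective. Each exit then falls in one group only. For example, with 12 placed, one accessory-related exit and one other exit, and the remaining ten effective, the scored result is 10/11 = 90.9% with one exit listed, and the sensitivity result is 10/12 = 83.3%.
5. In the withdrawal section, change *may* to *will* for data collected up to withdrawal, in agreement with Study Duration and Table 3.

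This needs no extra patients or visits. The cost is an amendment to wording and a reported success rate that may be slightly less favourable.

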 - o Curvature and ribs to prevent accessory component from migrating
 - Indented to retention bumper
- Retention accessory bumper
 - Cupped, to allow greater mobility of flexible tubing
- Introducer
 - A double tapered plastic rod to assist the stoma site accessory plug onto the feeding tube. One end will insert into the distal end of the feeding tube. The accessory plug will be put onto the opposite end of the introducer and slide toward feeding tube.

Duration of implant or exposure

The average life span of PEG tubes is reported to be three months with tube degradation being the primary reason for replacement.[5] The study stoma site accessory is anticipated to be compatible with this duration based on similar SOC flange and button accessories. Maximum duration is unknown but could be significantly longer. Many commercial insurers will cover up to four tube replacements per calendar or rolling year. For study purposes the maximum length of time during which data will be collected for tubing change, as ordered by the treating physician, will be 6 months from initial study accessory placement.

[figure not shown]

Fig7. The study stoma site accessory depicting prevention of stomach acid from leaking on the abdominal wall.

Labeling/Accessory Tracking

The study stoma site accessory components will be sterilized by Cleveland Clinic's OR Surgical Processing Department. One retention bumper and one introducer will share one package since they are identical respectively in size. The accessory plug component will be in a separate package, labeled by size compatibility, e.g., "16 Fr, 20 Fr". All components will be double wrapped, barcoded and assembled as kits. Kits will be delivered for accountability and storage at room temperature in the Internal Medicine Research Unit (IMRU) located on the Cleveland Clinic (CC) Main Campus study site. Kits will be secured in a locked cabinet, accessible only to study personnel. Study personnel will maintain and monitor usage on a Case Report Form. IMRU study personnel can readily provide the study stoma site accessory kits to any procedure area on the Main Campus at short notice.

Manufacturing Information

Dow Corning® QP1-250

Dow Corning Corporation

Technical Data

Product Description

Liquid Silicone Rubber materials for device and component fabrication in the healthcare industry

APPLICATIONS

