Patients meeting all of the inclusion criteria and none of the exclusion criteria may be invited to participate in the study. The study plan, potential risks and benefits of participation in the study and authorization for optional abdominal photos at the time of consent, week 2, and months 3 and 4, seen in Table 1, page 22, will be explained to all patients eligible for entry into the study. Patients can be consented up to 30 days in advance of their scheduled replacement procedure, using the IRB approved consent. Patients who require sedation for the procedure will not be eligible for the study stoma site accessory. All patients should be familiar with the Informed Consent and its content, and have been given opportunity to have their questions answered about the study prior to signing the Informed Consent as well as given the choice to decline consent. Each patient who decides to participate will be required to sign an Informed Consent document prior to any study-related procedures, including additional authorization or opt-out for abdominal photos. Patients can sign the Informed Consent in advance and be declined participation on the day of procedure if the attending physician determines them unfit for replacement with the study stoma site accessory.

If new information is obtained after a patient receives treatment with the device, patients who have not exited the study will be informed about the new information and will be re-consented at the discretion of the site's IRB.

Patients will undergo a baseline evaluation including the following:

- General assessment of the Abdomen with stoma site inspection
- Clinical assessments for confirmation of inclusion / exclusion criteria

ENROLLMENT SCHEMA

An overview of the study activities is presented in Table 1 Schedule of Events

Follow-Up

Patients are expected to participate in this study for up to 6 months after the index procedure. The follow-up visits and phone calls should occur within the following time frames when possible. Follow-up time frames are intended as guidelines only. They are not absolute and are not intended to limit data collection due to scheduling conflicts.

```
2 week (14 \pm 3 days; 11-17 days after the index procedure)
4 week (28 \pm 3 days; 25-31 days after the index procedure)
6 weeks(42 \pm 3 days; 39-45 days after the index procedure)
3 month (84 \pm 3 days; 81-87 days after the index procedure)
4 month (112 \pm 3 days; 109-115 days after the index procedure)

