6 month (180 \pm 7 days; 173-187 days after the index procedure)
```

The follow-up visit at 2 weeks can be scheduled as in-person or a virtual visit and will include:

- General Assessment of the abdomen with stoma site inspection
- Characteristics of pain and leakage questionnaire
- Abdominal Pictures
- Medications of Interest
- Oral Temperature Log Review
- Oral Temperature
- Adverse events

The follow-up phone calls at weeks 4, 6 and after an unscheduled visit will include the following:

- Characteristics of pain and leakage questionnaire
- Medications of Interest
- Adverse events

The follow-up visit at months 3 and 4 will be virtual or in-person and include:

- General Assessment of the abdomen with stoma site inspection
- Characteristics of pain and leakage questionnaire
- Abdominal Pictures
- Medications of Interest
- Oral Temperature
- Adverse events

The follow-up visit at month 6 will be in-person and include:

- General Assessment of the abdomen with stoma site inspection
- Feeding tube change with removal of study device and replacement with SOC tubing
- PROMIS 10
- Tobacco use questionnaire
- Characteristics of pain and leakage questionnaire
- Medications of interest
- Adverse events

If early termination occurs, study personnel will attempt to collect the following:

- General Assessment of the Abdomen with stoma site inspection
- PROMIS 10
- Tobacco use questionnaire
- Characteristics of pain and leakage questionnaire
- Medications of Interest
- Vitals

Any unscheduled visits discovered during follow-up phone calls or patient reported will be recorded on the appropriate case report form (CRF); The reason for the visit, adverse events of interest, treatments, interventions, hospitalizations and those resulting in early termination will be captured.

A Study Completion CRF should be completed at Month 6. The Investigator also must provide follow-up medical care for all patients who are prematurely withdrawn from the study, or must refer them for appropriate ongoing care.

SCREEN FAILURES

Participants who are consented to participate in the clinical trial, who are scheduled for enteral feeding tube replacement with the study stoma site accessory and who are determined by the attending clinician investigator at the time of intervention to be inappropriate candidates for anatomical or medical reason, e.g., requiring sedation, not previously ascertained during the screening procedures, are considered screen failures.

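### No contact is scheduled between the month 4 visit (day 112) and the month 6 visit (day 180), so minor events in the last 38% of follow-up rest on recall or self-report

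*Combined protocol and SAP*

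**What the plan says.** The Follow-Up section lists contacts at weeks 2, 4 and 6 (the last at "39-45 days after the index procedure"), month 3 ("81-87 days after the index procedure"), month 4 ("109-115 days after the index procedure") and month 6 ("173-187 days after the index procedure"). It adds that "Follow-up time frames are intended as guidelines only". Table 1 (Schedule of Events), the synopsis and the Study Duration section add no contact between months 4 and 6.

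Telephone contacts are defined by: "The follow-up phone calls at weeks 4, 6 and after an unscheduled visit will include the following". Their content is the pain and leakage questionnaire, medications of interest and adverse events.

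Table 3, under Primary Outcome Measures, sets the safety endpoint: "Rate of post-procedure adverse events to be collected from initial replacement procedure through month 6". It names dermatitis and cellulitis among the events, and its objective column puts the focus on minor risks linked to tube leakage.

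On duration of wear, the protocol states: "The average life span of PEG tubes is reported to be three months". It expects the accessory to be compatible with that duration and gives its maximum duration as unknown. The list of risks includes long-term risks as unknown.

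**The concern.** This is a first-in-human accessory, and the later months of wear are the least characterised. They are also the least observed: contacts are two weeks apart up to week 6, whereas the final interval has none for more than two months. The abdominal pictures, which are optional, also stop at month 4.

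The endpoint targets events that are often minor and short. A patient who has ten days of leakage, changes dressings at home and recovers produces no visit, no chart entry and no accessory removal. If that happens between days 113 and 179, the study learns of it only if the patient calls in or recalls it at month 6. What is at stake is the completeness of the primary adverse-event rate in that period. With about 10 patients and endpoints reported as percentages, one patient whose only event goes unrecorded would move a per-patient rate by 1/10, or 10 percentage points.

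**Working it through.** **Inputs.** Nominal days and windows come from the Follow-Up section: 14, 28, 42, 84 and 112 (each ±3) and 180 (±7). The printed ranges agree with these tolerances, for example 112 − 3 = 109 and 112 + 3 = 115; 180 − 7 = 173 and 180 + 7 = 187. The plan does not state the intervals between contacts.

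**Step 1: intervals between scheduled contacts.**

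| From – to | Nominal days | Within windows | Share of 180 days |
|---|---|---|---|
| Day 0 – week 2 | 14 | 11–17 | 8% |
| Week 2 – week 4 | 14 | 8–20 | 8% |
| Week 4 – week 6 | 14 | 8–20 | 8% |
| Week 6 – month 3 | 42 | 36–48 | 23% |
| Month 3 – month 4 | 28 | 22–34 | 16% |
| Month 4 – month 6 | 68 | 58–78 | 38% |

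The last row is 180 − 112 = 68 and 68/180 = 37.8%. Its extremes are 173 − 115 = 58 and 187 − 109 = 78.

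**Step 2: how much is due to month length?** 84/3 = 28, 112/4 = 28, but 180/6 = 30. With one convention throughout, the month 4 to month 6 interval would be:
- 28-day months: 168 − 112 = 56 days
- 30-day months: 180 − 120 = 60 days
- 30.44-day months: 2 × 30.44 ≈ 61 days

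The mixed convention therefore adds 68 − 61 = 7 to 68 − 56 = 12 days. The remaining 56 to 61 days exist because there is no month 5 contact.

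**Step 3: position relative to three months.** Three months is about day 90–91. Day 84 lies before it and day 112 lies 21–22 days after it.

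**Step 4: share of episodes still present at the next scheduled contact.** Assume onset is uniform over an interval of G days and the episode lasts L days (L ≤ G). It is still present at the next contact if it starts in the last L days, so the share is L/G. The documents give no episode duration, so a range is shown.

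| Episode length (assumed) | Week 6 – month 3 (G = 42) | Month 4 – month 6 (G = 68) | With a midway call (G = 34) |
|---|---|---|---|
| 7 days | 17% | 10% | 21% |
| 14 days | 33% | 21% | 41% |
| 21 days | 50% | 31% | 62% |

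At the window extremes, the 14-day share is 14/78 = 18% to 14/58 = 24% for the last interval, and 14/48 = 29% to 14/36 = 39% for week 6 to month 3.

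**Step 5: recall.** The midpoint is (112 + 180)/2 = day 146. The longest nominal recall falls from 68 to 180 − 146 = 34 days.

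**The case against.** The strongest reply is that the interval is not unobserved. Adverse events are collected over the whole study, and the in-person month 6 visit includes inspection, adverse events and the pain and leakage questionnaire. Unscheduled visits are recorded and followed by a call, charts and outside records are reviewed, and patients are asked to make contact within 48 hours of a qualifying event. Accessory removal is given there as an example, not as a limit. The protocol also describes leakage as a common reason for requesting a tube change, so troublesome leakage would tend to generate a visit. This is a small descriptive pilot, and contact frequency is partly a matter of preference.

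Much of this stands, and it rules out several stronger readings that a reader might infer:

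- *Late events are missed.* Not supported. The percentages in Step 4 are shares still present on a contact day, not shares detected; recall, self-report and records add to them.
- *Early episodes are all seen.* Dividing 14 by 14 gives 100% for weeks 2 to 6, but the windows allow 20 days between those contacts (14/20 = 70%), and the 42-day interval before month 3 gives only 33%.
- *Inconsistent months create the gap.* They account for 7 to 12 of 68 days.
- *The gap opens just as the tube reaches its stated life.* Visits at days 84 and 112 lie on either side of that point, and three months is a reported average for PEG tubes, not a limit for the accessory.
- *The accessory will look more durable than shown.* Removal or re-intervention that compromises it ends follow-up and has its own reporting route, so those failures do not depend on recalling mild irritation.

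What the reply does not answer is the self-managed episode. The routes between visits mainly catch events that led to care or removal, and the document states no look-back period for the month 6 questions.

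**Conclusion.** The concern holds in a limited form. Minor, self-managed events with onset and resolution between days 112 and 180 count toward the primary adverse-event rate but depend on self-report or on recall of up to 68 days nominally (78 within the windows), so they are at risk of under-recording.

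The 68-day interval is plain arithmetic, although actual intervals may differ because the windows are only guidance. The 21% and 41% rest on an assumed 14-day duration and uniform onset; they show the scale of reliance on recall and do not estimate events lost. The questionnaire and case report forms are not reproduced in the document, so a look-back may already be written there. This is a worthwhile, inexpensive improvement to a primary safety endpoint, not a defect that undermines the study.

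**What to change.** 1. Add one scheduled phone call midway between the month 4 and month 6 visits to Table 1 and the Follow-Up section, using the existing week 4 and 6 script. That is about day 146 if month 4 stays at day 112. If month 4 moves to day 120, it is about day 150; the two intervals are then 30 days each and the 14-day share is 14/30 = 47%.
2. Word the month 6 adverse-event and leakage questions so that they ask explicitly about the whole period since the last contact. This helps even if the call is not adopted.
3. Optionally, relabel days 84 and 112 as weeks 12 and 16. This is clerical and does not close the gap.

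Cost: about 10 scripted calls in total by existing coordinators, one more column in Table 1 and a small amendment. Table 2 lists no payment for the existing phone calls. No visit or procedure is added.
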